3.2. Study Design Rationale

Vector Selection

The rationale behind the selection of the Ad26 vector is described in Section 1.1.

Dose Selection

The rationale behind the selection of the Ad26 dose is described in Section 1.1.

Rationale for Vaccine Regimen Selection

The active vaccine for this study was determined from the primary analysis of Cohort 2 in Study VAC18193RSV1004.

Blinding, Control, Study Phase/Periods, Intervention Groups

A placebo control will be used to establish the frequency and magnitude of changes in clinical endpoints that may occur in the absence of active intervention. Randomization will be used to minimize bias in the assignment of participants to vaccine groups (ie, active vaccine [Group 1] or placebo [Group 2] for all participants in Cohort 1, and assignment to Ad26.RSV.preF/RSV preF protein mixture or the individual vaccine components for Revaccination Subcohorts 2A and 2B), to increase the likelihood that known and unknown participant attributes (eg, demographic and baseline characteristics) are evenly balanced across groups, and to enhance the validity of statistical comparisons across groups. Blinded intervention will be used to reduce potential bias during data collection and evaluation of clinical endpoints.

For the Revaccination Subcohorts, all participants will receive active study vaccine at the time of revaccination. The blinding for the study vaccine received on Day 1 will be maintained for the site and participants until the database lock for the final analysis of the considered cohort, except for Revaccination Subcohorts A and B, who will be unblinded to the Day 1 vaccination prior to re-randomization to the third vaccination: participants who received active vaccine on Day 1 will complete the study at that time, participants who received placebo on Day 1 will be re-randomized to receive either Ad26.RSV.preF/RSV preF protein mixture or the individual vaccine components in a blinded fashion.

Medical Resource Utilization Data Collection

Prophylaxis of RSV infection may reduce the need for and duration of supportive care (eg, hospitalization, oxygen supplementation, etc.). The study will evaluate the impact of active study vaccine versus placebo on the development and clinical course of RSV disease.

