- Come to the site between 2 and 4 days after symptom onset (ARI Days 3-5), or, if a site visit is not feasible, a member of the study staff can visit the participant at home (or at the hospital, if needed) during this time frame.
- Between 2 and 4 days after symptom onset (ARI Days 3-5), a midturbinate nasal swab, a sputum sample (in participants with a productive cough, when possible) and a blood sample for seroconfirmation and exploration of biomarkers that correlate with RSV infection and RSV disease severity will be taken by a qualified member of the study staff, and vital signs, including body temperature, blood pressure, heart rate, respiratory rate and oxygen saturation, will be measured. A clinical assessment, including a targeted physical examination, will be completed by qualified study staff, preferably by a physician, physician assistant, nurse practitioner, or equivalent. The participant's functional status will also be evaluated by the Lawton-Brody IADL questionnaire. The MRU questionnaire will be completed based on clinical interview. The participant will complete all 4 scales of the RiiQ v2 questionnaire on the site's eDevice and provide the study staff member the midturbinate nasal swab collected by the participant at home.
- At ARI Day 29 (± 7 days), participants will be asked to return to the site where a blood sample will be drawn for seroconfirmation and exploration of biomarkers that correlate with RSV infection and RSV disease severity. A qualified member of the study staff will measure vital signs, including body temperature, blood pressure, heart rate, respiratory rate and oxygen saturation. A clinical assessment (including a targeted physical examination) will be performed by qualified study staff, preferably by a physician, physician assistant, nurse practitioner or equivalent, and the Lawton-Brody IADL assessment and MRU questionnaire will be completed based on interview with the participant. Participants will complete all 4 scales of the RiiQ questionnaire, and each of the PGI scales and the Return to Usual Health question on the site's eDevice.

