11.4. Efficacy Analyses

11.4.1. Primary Efficacy Endpoints

Three primary efficacy endpoints are defined as follows:

- First occurrence of RT-PCR-confirmed RSV-mediated LRTD according to Case Definition #1
- First occurrence of RT-PCR-confirmed RSV-mediated LRTD according to Case Definition #2
- First occurrence of RT-PCR-confirmed RSV-mediated LRTD according to Case Definition #3

The case definitions are defined as follows:

Case Definition #1	Case Definition #2	Case Definition #3
≥3 symptoms of LRTI (new onset or worsening)	≥2 symptoms of LRTI (new onset or worsening)	≥2 symptoms of LRTI, OR ≥1 symptom of LRTI combined with ≥1 systemic symptom
		(new onset or worsening)

LRTI = lower respiratory tract infection

To meet the primary endpoint according to the respective case definitions the following criteria will be taken into account:

- symptoms reported by participants on the RiiQ Symptom Scale and body temperature during the full ARI episode OR
- clinical assessment terms reported by a qualified study staff member during the ARI Days 3-5 clinical visit

in combination with

- confirmation of RSV by RT-PCR in one or more of the midturbinate nasal swabs, or in the sputum sample (when available)

Of note, on the day of the ARI Days 3-5 clinical visit, the case definitions can be met by symptoms reported by participants on the RiiQ or by signs and symptoms reported by the qualified study staff member. Case definitions cannot be met by a combination of symptoms reported by the participant with signs and symptoms reported by the qualified study staff member.

Confirmation of RSV infection by RT-PCR (midturbinate swabs and sputum sample, when available) will be performed at the central laboratory. For participants hospitalized with symptoms of an ARI, confirmation of RSV infection using an FDA-approved RT-PCR test at the local (hospital) laboratory will also be used for the analysis of case definitions if results from the central laboratory are not available. One positive sample (defined as any sample with a value above the limit of detection) is sufficient.

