As a sensitivity analysis, the analysis of the primary endpoint will be repeated, but participants with RSV infection and a co-infection with at least one other respiratory virus (ie, confirmed using an FDA approved RT-PCR test in one or more of the midturbinate nasal swabs, or in the sputum sample, when available) will not be considered as a case for that episode, as the etiology of the symptoms will be indeterminate.

As an additional sensitivity analysis, the analysis of the primary endpoint will be repeated, taking into account only the RT-PCR test results from the central laboratory (ie, excluding the local test results for hospitalized participants).

Presence and severity of symptoms will be collected using participant responses to the RiiQ Symptom Scale and temperature readings participants report in the eDiary each day throughout each ARI episode. On the day of the ARI Days 3-5 clinical visit, signs and symptoms will also be collected by qualified study staff in a clinical assessment.

Table 11: Symptoms of Lower Respiratory Tract Infection and Systemic Symptoms as per RiiQ or Clinical Assessment

	Symptoms from Case Definition	RiiQ Term	Clinical Assessment Term (ARI Days 3-5 Clinical Visit)
Symptoms of LRTI	Cough	Cough	Cough
	Shortness of breath	Short of breath	Dyspnea or decreased oxygen saturation*
	Sputum production	Coughing up phlegm (sputum)	Sputum production
	Wheezing	Wheezing	Wheezing; rhonchi, rales or other sign of consolidation
Systemic Symptoms	Tachypnea**		Tachypnea
	Fatigue	Fatigue (tiredness)	Malaise (tiredness)
	Fever***,****		Fever
	Feverishness****	Feeling feverish	

* Decreased oxygen saturation is defined as oxygen saturation of <90% for participants with a baseline oxygen saturation of $\geq 90\%$ at randomization; for participants with baseline oxygen saturation <90%, decreased oxygen saturation is defined as a $\geq 3\%$ decrease in their oxygen saturation from baseline.

** Tachypnea is defined as respiratory rate >20 breaths per minute.

*** Fever (ie, temperature >37.8°C) will be reported via daily temperature measurement and during ARI Days 3-5 clinical visit.

**** Feeling feverish and fever are considered as 1 symptom.

LRTI =lower respiratory tract infection, RiiQ = Respiratory Infection Intensity and Impact Questionnaire

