This is defined similarly as the primary endpoint but taking into account events over the 2 or 3 seasons. The baseline assessment for the second RSV season is the Day 365 (Month 12) visit and for the third RSV season it is the Day 730 (Month 24) visit. New onset or worsening is defined similarly as for the primary endpoint, by comparing symptoms occurring during the ARI episode to symptoms reported at the new baseline (instead of comparing to Day 1). When evaluating the vaccine efficacy over 2 and 3 seasons, first occurrence of a considered endpoint over 2 or 3 seasons is defined as the first episode of the considered over the considered period (2 RSV seasons or 3 RSV seasons respectively, regardless A or B strain, unless otherwise specified).

Other secondary or exploratory objectives that were assessed during the first RSV season (as defined in section 11.4.2 and below), might also be explored during the second and the third RSV season and over 2 and 3 RSV seasons. These endpoints are defined similarly as the corresponding endpoints during the first RSV season, but baseline, new onset or worsening, and first occurrence are defined in a similar way as for RT-PCR-confirmed RSV-mediated LRTD, during the second and the third RSV season and over 2 or 3 RSV seasons (see above).

- First occurrence of any RT-PCR-confirmed RSV disease caused by an RSV A or RSV B strain, respectively
- First occurrence of potential complications of respiratory disease (eg, pneumonia, new onset, worsening, or an exacerbation of CHF, asthma, and COPD) linked to any respiratory disease and linked to any RT-PCR confirmed RSV disease
- Efficacy of active study vaccine against other respiratory diseases
Midturbinate nasal swabs may be tested for the presence of other respiratory pathogens
- First occurrence of hospitalization linked to any respiratory disease and linked to any RT-PCR confirmed RSV disease
- Determination of oxygen saturation during clinical assessment during ARI episodes
- First occurrence of RT-PCR-confirmed RSV-mediated LRTD according an ordinal case definition

The ordinal case definitions are provided in [Table 12](#).

Table 12: Ordinal Case Definition

Ordinal Case definition	Ordinal variable	Participants fulfilling
≥3 symptoms of LRTI (new onset or worsening), in combination with confirmation of RSV by RT-PCR in one or more of the midturbinate nasal swabs, or in the sputum sample (when available)	4	Case Definition 1, 2 and 3

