Was another diagnostic method used?		 Yes  No
If yes, please specify diagnostic method: _____		
Date performed: _____		
Specify results: _____		
Do the results support a diagnosis of LRTD?		 Yes  No

SUPPLEMENTAL OXYGEN		
Was supplemental oxygen administered?		 Yes  No
If 'yes' selected, please fill out remaining questions in this section.		
Type of supplemental oxygen administration:		
 Invasive Mechanical Ventilation		 Venturi Mask
 Non-Invasive Mechanical Ventilation		 Simple Face Mask
 Nasal Cannula		 Reservoir Cannulas
 Nonrebreathing Face Mask with Reservoir and One-Way Valve		
 Other: _____		
If invasive mechanical ventilation, specify:		
 Through endotracheal tube		 Through tracheostomy tube
If non-invasive mechanical ventilation, specify:		
 Continuous positive airway pressure		 Bilevel positive airway pressure
Oxygen concentration and units: _____		
Start date and time: _____		

End date and time (if applicable): _____

Has supplemental oxygen administration returned to that level provided prior to the current respiratory illness?

Yes No

Below question only to be completed if patient has history of COPD or asthma.

If applicable, does requirement for oxygen supplementation or increased oxygen supplementation support a diagnosis of a COPD or asthma exacerbation?

COPD exacerbation asthma exacerbation No

ADDITIONAL COMMENTS

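### SpO2 counts at its measured value even if the participant is on supplemental oxygen, so corrected hypoxaemia scores as normal in Table 11 and in the exploratory oxygen-saturation endpoint

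*Protocol*

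**What the plan says.** All references are to the Protocol.

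- **Case definition (Section 11.4.1, Table 11).** On the staff-assessed route, the shortness-of-breath item is met by "Dyspnea or decreased oxygen saturation". The footnote reads "Decreased oxygen saturation is defined as oxygen saturation of <90% for participants with a baseline oxygen saturation of" 90% or more; "for participants with baseline oxygen saturation <90%, decreased oxygen saturation is defined as a" drop of 3% or more. The rule depends on baseline saturation, not on oxygen therapy.
- **Measurement.** The ARI schedule (footnote h) asks for at least 5 minutes' rest and Section 9.2.4.2 for rest in a quiet setting. Neither mentions room air. The Attachment 3 form has one SpO2 line and no entry for oxygen status.
- **Exploratory endpoint (Section 11.4.3).** "Determination of oxygen saturation during clinical assessment during ARI episodes". Section 2.1 lists oxygen saturation under the objective on the course of respiratory disease, and Section 11.4.3.1 summarises continuous endpoints as actual values and, if meaningful, changes from baseline.
- **Setting (Section 9.1.1).** If a site visit is not feasible, "a member of the study staff can visit the participant at home (or at the hospital, if needed").
- **Expected effect (Section 3.2).** "Prophylaxis of RSV infection may reduce the need for and duration of supportive care (eg, hospitalization, oxygen supplementation, etc".
- **Oxygen data.** Section 9.1.1 asks sites to collect oxygenation status and supplemental oxygen needs during an ARI. Attachment 12, Section 2, asks "Was supplemental oxygen administered" and records type, concentration, and start and end times.

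**The concern.** SpO2 read on oxygen measures the disease and its treatment together. The protocol allows the assessment to take place in hospital, where oxygen is most likely to be in use, and then applies a fixed threshold to whatever the oximeter shows. A participant who would be below 90% untreated but reads 90% or above on oxygen does not have the sign, and looks the same in the summary as a participant who was never hypoxaemic.

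The trial exists to show less, and less severe, disease in the vaccine arm. If it succeeds, corrected readings should be more numerous under placebo. The exploratory SpO2 comparison would then understate a real benefit. A placebo case could also, by a narrow route, miss a case definition.

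**Working it through.** **1. Scoring under the rule as written (baseline 90% or more)**

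| State at the Days 3-5 assessment | Has the sign? | Enters the SpO2 summary as |
|---|---|---|
| Below 90%, no oxygen | Yes | Low |
| Still below 90% on oxygen | Yes | Low |
| Corrected to 90% or above on oxygen | No | Normal |
| Never hypoxaemic | No | Normal |

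The third row is misclassified. With a baseline under 90% the same happens when oxygen prevents the 3% fall.

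**2. Direction of bias in the SpO2 endpoint**

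Let *h* be the proportion of assessed episodes with hypoxaemia, counting those corrected by oxygen, and *o* the share of these that are corrected. The observed proportion below threshold is *h*(1 − *o*).

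- If *o* is the same in both arms, the observed difference is (1 − *o*)(*h*_placebo − *h*_vaccine). The absolute difference shrinks and the ratio is unchanged.
- If *o* is larger under placebo, the ratio moves toward 1 as well.

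The protocol gives neither *h* nor *o*, so the size cannot be computed.

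**3. What it takes to lose a primary case**

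For Case Definition #1 (at least 3 LRTI symptoms), all of these must hold:

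- hypoxaemia is corrected by oxygen at the Days 3-5 assessment;
- staff record no new or worsened dyspnea;
- exactly two other LRTI signs are recorded by staff;
- the participant's own RiiQ reports never reach three LRTI symptoms on any one day of the episode.

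Such a participant has two LRTI signs and so still meets #2 and #3. One step lower, with a single other LRTI sign, #2 is missed, and #3 is met only if a systemic symptom is also recorded.

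**4. Scale for the primary analysis, under assumed loss**

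The plan's own figures come first. Inputs from Section 11.2.1: 2,750 per group, 10% exclusions, placebo incidence 0.75%, VE 70%, one-sided α 5%.

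- Placebo cases: 2,750 × 0.90 × 0.0075 = 18.56.
- Vaccine cases: 18.56 × 0.30 = 5.57. Total 24.1.
- With 2,900 per group the total is 25.4; with 2,750 and no exclusions, 26.8. The protocol states 26, within 2 of each.
- Power by the exact conditional binomial test at 0.05, averaged over a Poisson number of events, is 81.7%, against 80% stated.

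Now suppose a fraction of Case Definition #2 cases is lost through the oxygen route. The fractions are assumptions.

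| Cases lost | Apparent VE | Power |
|---|---|---|
| None | 70% | 81.7% |
| 2% in both arms | 70% | 80.9% |
| 5% in both arms | 70% | 79.7% |
| 10% in both arms | 70% | 77.4% |
| 5% in placebo only | 1 − 0.30/0.95 = 68.4% | 77.3% |
| 10% in placebo only | 1 − 0.30/0.90 = 66.7% | 72.1% |

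Equal loss costs power but does not bias VE. Bias needs unequal loss. Given the conditions in step 3, the placebo-only rows are stress cases rather than expectations.

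**The case against.** The strongest reply is that this is inferred from silence. No sentence says that readings on oxygen are used unadjusted, and flagging them in a descriptive exploratory table is ordinary SAP detail. That stands in part: the SAP, which is not among the documents reviewed, could set a rule for the summary. It does not dispose of the case-definition criterion, which the protocol itself fixes by the measured value.

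A reader might infer that the plan hides the most severe cases. The documents do not support that. Low SpO2 is only an alternative to dyspnea within one item on one of two routes. The other route uses "symptoms reported by participants on the RiiQ Symptom Scale and body temperature during the full ARI episode OR" the staff assessment, and Section 9.1.1 lets staff read the questions to a participant who cannot complete the eDiary. Hospitalization and complications are separate endpoints, and the severity evaluation draws on the CEC review and therapeutic interventions. A small gap remains: the two routes cannot be combined, and a participant on invasive ventilation, which Attachment 12 lists, cannot answer questions. An earlier qualifying RiiQ day would still count.

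A reader might also infer that every oxygen-treated episode is misread. That is wrong: a reading still below 90% on oxygen counts, and oxygen given only before or after the assessment leaves the reading untouched.

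Nor should the protocol's wording be overstated. Section 3.2 says vaccination may reduce oxygen use, and Section 9.1.1 permits a hospital assessment but does not predict how many will occur.

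**Conclusion.** The point holds as a minor one. Followed as written, the SpO2 criterion and the exploratory SpO2 endpoint classify oxygen-corrected hypoxaemia as normal, although oxygen use is recorded elsewhere.

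For the SpO2 endpoint, the likely direction is toward no difference if vaccination reduces oxygen use. On the ratio scale this also requires a larger corrected share under placebo. The size is unknown.

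For the primary endpoints the effect is likely small. Nothing in the documents suggests that proof of concept hangs on it: success needs only one of the three definitions, and a case lost from #1 by one sign remains in #2 and #3. The VE and power figures above rest on assumed loss fractions and are not estimates.

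**What to change.** Leave the primary case definitions and their analysis unchanged. Using the ARI clinical-course data and the Attachment 12 oxygen times:

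1. For the exploratory endpoint, analyse by arm a composite of SpO2 below the Table 11 threshold or new or increased supplemental oxygen on the assessment day.
2. Summarise raw SpO2 only for readings not known to be on new or increased oxygen, and report by arm how many are set aside.
3. Repeat the three case definitions with the composite in place of decreased oxygen saturation, as a sensitivity analysis only.

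The cost is one derived variable, one table and one rerun, with no new data collection. There are two drawbacks. The composite partly reflects local oxygen practice. The Attachment 12 oxygen section covers only emergency-department and hospital care, is completed by outside providers and may be incomplete, so some oxygen use will be missed.

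An oxygen-status box on Attachment 3 is worth adding only if more ARI data will be collected. Amendment 8 is dated 16 February 2023, and the last stated surveillance cut-off is 15 April 2022.

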11.4.1.1. Analysis

Any analysis of the primary endpoints for VE will evaluate the number of participants with (at least one episode of) RT-PCR-confirmed RSV-mediated LRTD (cases defined according to the 3 primary endpoint definitions) in the active vaccine group compared to the placebo group in the PPE population. Time at risk will also be taken into account. The null hypothesis of $VE \leq 0\%$ for all 3 primary endpoints will be tested versus the alternative hypothesis $VE > 0\%$ for at least one primary endpoint.

The α -levels for all efficacy analyses will be adjusted:

- To account for the multiple endpoint approach. The multiplicity correction method for the 3 primary endpoints is based on the approach by Spiessens and Debois.²⁶ The exact value will be calculated based on the number of events observed for each definition at the time of analysis, targeting the same α -level for each of the 3 primary endpoints.
- To account for multiple analyses (see Section 11.12 for details on the planned analyses):
 - use estimated proportion of events already observed (P_{IA}) and Pocock rule to set α' for the IA
 - P_{IA} obtained from epidemiological/disease transmission model and real world evidence (RWE)
 - *This α' will be equally divided across the 3 primary endpoints based on the observed incidence*

at the end of the study, based on Case Definition #2, calculate the actual information fraction (IF) at the IA based on the total number of events

- From this information and α' , calculate the α'' level for the final analysis.
- *This α'' will again be equally divided across the 3 primary endpoints based on the incidence of the 3 case definitions.*

Both methods will be combined to come to one cut-off that will be used to define significance. The exact values cannot yet be provided as they depend on the number of cases already observed at the time of (interim) analysis.

For example: assume in a NH and SH study an IA was performed with 18 RT-PCR-confirmed RSV-mediated LRTD events observed of the expected 26: the IFs for the interim and primary analyses are 0.7 and 1, respectively. With a total α of 0.05, the α at each analysis (IA and primary analysis) will be 0.0335 using Pocock's rule. If then at the IA the total number of events are as follows: 14 events with Case Definition #1, 18 events with Case Definition #2, and 25 events with Case Definition #3, the IFs at the IA are: 0.56, 0.72, and 1. Again, using Pocock's rule, the α for each individual case definition will be 0.0175. So, proof of concept will be declared at the IA if, for any endpoint, the comparison of the number of events on vaccine compared to placebo if the p-value is <0.0175 .

For each of the 3 primary endpoints the following will be performed: an exact Poisson regression will be fitted with the event rate, defined as the number of cases over the follow-up time (offset) as dependent variable and the vaccination group and age and being at increased risk for severe RSV disease (both as stratified) as independent variables. For cases, the follow-up time is defined as the time between vaccination and the occurrence of the first event (according to the considered endpoint), for non-cases, it is the time between vaccination and the end of season visit. However, for participants that discontinued before the end of the season and had an event (according to the considered endpoint), the follow-up time is defined as the time between vaccination and the occurrence of the first event and for participants that discontinued before having an event, follow-up time is the time between vaccination and the date of last contact. Thus, all participants are included in the analysis according to their follow-up time. The exact p-value corresponding to vaccination group will be compared with the cut-off as described above.

If the p-value is below the cut-off for at least 1 of the 3 primary endpoints, proof of concept is demonstrated. The individual 2-sided CIs ($1-2 \times \text{cut-off}$) for the VE (1-relative risk rate), measured by each of the 3 endpoints, will be calculated from the regression model described above.

The primary analysis will be performed on the PPE population, which will take cases into account with an onset at least 14 days after vaccination.

As a sensitivity analysis, the above model will be repeated based on the FAS (which also does not take into account the restriction on the onset [at least 14 days] and will count cases from vaccination on Day 1 onwards). Additional sensitivity analyses will include an exact binomial test, not taking into account the strata, based on the PPE population and the FAS. The VE (1-relative

risk) and the corresponding corrected 2-sided CI based on the exact binomial will be calculated as well.

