3. STUDY DESIGN AND RATIONALE

3.1. Overview of Study Design

This is a multi-center, randomized, double-blind, placebo-controlled Phase 2b proof-of-concept study in male and female participants aged ≥ 65 years who are in stable health. A target of up to 5,800 participants (Cohort 1) will be enrolled and randomized in parallel in a 1:1 ratio to 1 of 2 groups to receive active study vaccine (Group 1) or placebo (Group 2) intramuscularly (Table 2).

Based on the primary analysis of safety and immunogenicity results from Cohort 2 in Study VAC18193RSV1004 (immunogenicity including, but not limited to RSV neutralizing antibodies), a sponsor committee has selected the study vaccine dose and regimen to be used in this study. In making the selection, additional factors such as data from other assays, cost of goods, and ease of administration were also taken into account.

The study comprises administration of an Ad26.RSV.preF/RSV preF protein mixture (or placebo) to be administered as a single injection on Day 1. After vaccination, participants will be followed for symptoms that could indicate an ARI until the end of the RSV season. The end of the first NH RSV season for the onset of an ARI is defined as 20 March 2020 (due to the coronavirus disease 2019 [COVID-19] pandemic, Amendment 2), the end of the second NH RSV season for the onset of an ARI will be defined as 17 May 2021, and the end of the third NH RSV season for the onset of an ARI will be defined as 15 April 2022^a. The end of the SH RSV season is country/territory-specific and will be specified to the sites prior to the start of dosing in the SH. Study progression

^a The defined end-of-season dates for the second and third NH RSV season may be updated in case there would be indications of a shift in season.

beyond the first and second RSV seasons is conditional on the results obtained at the end of each of these RSV seasons.

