11.2. Sample Size Determination

11.2.1. Efficacy

Under the following assumptions:

- a VE for Case Definition #2 of 70%
- and an incidence of Case Definition #2 of 0.75% in placebo recipients during the RSV season, assuming vaccination occurs before the RSV season
- 3 primary endpoints which are nested (see Section 11.4.1)
- a 1-sided α of 5% (total: as described in Section 11.4.1.1, corrections are performed for multiple endpoints and for IAs outlined in Section 11.12)
- 10% of exclusions (due to drop-out, major protocol deviations, etc.)

Simulations performed in R show that for a NH only study, 2,750 participants per vaccination group result in 80% total power to demonstrate $VE > 0$ for Case Definition #2 at the end of the RSV season, resulting in a total sample size of 5,500 participants. The end of the first RSV season is then defined as the end of the NH RSV season.

In case recruitment is not completed in the NH (and less than 18 RT-PCR-confirmed RSV-mediated LRTD events (using Case Definition #2) are observed in the NH before opening sites in the SH), enrollment will continue in the SH. As there is the possibility to have an early IA during the NH or SH RSV season (see Section 11.12), an additional 150 participants per vaccination group is needed to have 80% total power to demonstrate $VE > 0$ for Case Definition #2 at the end of the RSV season. The end of the first RSV season is defined as the end of the SH RSV season in case the study is performed at both hemispheres. So, if recruitment is spread over 2 hemispheres, the total sample size will be 5,800 participants.

With respect to Case Definitions #1 and #3, further simulations showed that the power to obtain a significant result for any case definition, after multiplicity correction that control the type I error at 5%, tended to be similar or better than for Case Definition #2 alone, without multiplicity correction. This result was valid over a broad range of incidence and vaccine efficacies, unless the VE for the most common case definition (Case Definition #3), was $> 20\%$ lower than the VE for Case Definition #2. Case Definition #2, which incidence lies between that of Case Definition #1

and #3, was chosen as basis for the power calculations and decision rule, as more prior information was available for this case definition in the literature. Under the assumptions described above, it is expected to observe 26 cases.

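### The common cut-off for the three nested primary endpoints is set by normal theory but applied to exact p-values on few events; the test stays valid, but a third or more of the allotted error goes unused and a little power is lost

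*Protocol*

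**What the plan says.** Section 11.2.1 plans for "a 1-sided α of 5" percent in total and for "3 primary endpoints which are nested". Success on any one of them establishes proof of concept.

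Section 11.4.1.1 adjusts α twice: over looks, with Pocock's rule, and over the three case definitions, targeting the same level for each. On the second step it says: "The exact value will be calculated based on the number of events observed for each definition at the time of analysis". Its worked example takes information fractions of 0.7 and 1 for the two looks and obtains 0.0335 per look. With 14, 18 and 25 events at the interim analysis the fractions for the definitions are 0.56, 0.72 and 1, and the α "for each individual case definition will be 0.0175".

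The test is an exact Poisson regression with a follow-up offset. The section then states: "The exact p-value corresponding to vaccination group will be compared with the cut-off as described above". Confidence intervals have level 1 minus twice the cut-off. No step allows for the discreteness of the exact p-value.

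**The concern.** A Pocock-type calculation assumes statistics that can reach any p-value. An exact p-value on 14 to 25 events takes only a few values near 0.0175, so the level attained for each definition falls to the nearest step below. The joint error over the three definitions then falls short of its budget. The trial pays for three endpoints and an interim look but does not spend all the error it set aside. With about 26 expected cases of Case Definition #2, one case can decide whether proof of concept is shown.

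**Working it through.** **Inputs.** From Section 11.2.1: one-sided total α 0.05; "a VE for Case Definition #2 of 70" percent; "an incidence of Case Definition #2 of 0.75% in placebo recipients during the RSV season"; 2,750 per group less 10% = 2,475; 26 expected cases. From Section 3.1: participants are "randomized in parallel in a 1:1 ratio to 1 of 2 groups". From Section 11.4.1.1: fractions 0.7 and 1, and 14/18/25 events.

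**Assumptions added here.** Equal follow-up, pooled strata and the same VE for all three definitions. Given a case, the chance that it is on vaccine is (1−VE)/(2−VE): 0.5 under the null and 0.3/1.3 = 0.231 at VE 70%.

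**1. The protocol's own figures.** Use normal statistics with correlation √(IFᵢ/IFⱼ) and equal one-sided levels.
- Looks at 0.7 and 1, total 0.05: 0.0335 per look, as stated.
- Definitions at 0.56, 0.72 and 1, total 0.0335: 0.0174 to 0.0175, as stated.

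So the cut-off is a normal-theory one.

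**2. What p<0.0175 admits.** The exact one-sided p-value for k vaccine cases among n is P(Bin(n, 0.5) ≤ k).

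| Definition | Events | Most vaccine cases allowed | Attained level | Next step |
|---|---|---|---|---|
| #1 | 14 | 2 | 0.0065 | 0.0287 (3/14) |
| #2 | 18 | 4 | 0.0154 | 0.0481 (5/18) |
| #3 | 25 | 6 | 0.0073 | 0.0216 (7/25) |

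**3. Joint exact error.** The nested counts are sums of independent binomials on 14, 18−14 = 4 and 25−18 = 7 cases. Summing over all splits that meet at least one limit gives 0.0197. That is 0.0197/0.0335 = 59% of the budget, so 41% is unused.

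**4. Exact calibration of the same look.** Admitting 7/25 raises the exact error to 0.0297, still within 0.0335. Admitting 3/14 as well gives 0.0427, which is over. At VE 70% the chance of success at this look rises from 71.1% to 81.4%. To five decimals the p-value at 7/25 is 0.02164. A limit of 0.0216 would therefore exclude it and change nothing. Any strict cut-off above 0.02164 and up to 0.0287 gives the same rule.

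**5. Both looks.** Scale the example to 26 cases: 14×26/18 ≈ 20 and 25×26/18 ≈ 36. The 20 and 36 are not in the protocol.

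| Looks 14/18/25, then 20/26/36 | Total exact error | Power, VE 70% |
|---|---|---|
| Current rule | 3.3% | 91.5% |
| Exact cut-offs | 4.75% | 92.8% |

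**6. A single season-end look at 5%.** Mean Case Definition #2 count 2,475 × 0.0075 × 1.3 = 24.1, Poisson totals in the ratio 14:18:25. The error used rises from about 3.3% to 4.2%, and power from about 89% to 91%. At exactly 20/26/36 the gain is larger (error 3.2% to 4.5%, power 91.4% to 95.2%), but that is one favourable set of counts.

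**7. The stated 80%.** An exact test of Case Definition #2 alone at 0.05, with 2,475 per group and Poisson events, gives 81.7%.

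**8. Calibrating each look on its own.** Filling each look's budget exactly, with the split between looks left on normal theory and 0.0335 at the interim, can overrun.

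| Interim, then final | Current rule | Each look calibrated separately |
|---|---|---|
| 12/17/19, then 19/27/37 | 2.7% | 5.15% |
| 14/15/18, then 16/17/24 | 3.4% | 5.31% |

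**The case against.** The strongest reply is that nothing here is invalid. A nominal boundary applied to exact p-values controls type I error, and Section 11.2.1 reports simulations in which power for any definition after correction was similar to or better than for Case Definition #2 uncorrected. The operating characteristics are in a separate report, and computational detail may be left to the SAP. Most of this stands: the point concerns efficiency. The SAP argument is weaker, because Section 11.4.1.1 itself fixes both the method, through a worked number, and the p-value it is applied to.

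Three stronger readings are tempting, and the documents support none of them.
- A reader might infer that the trial falls short of its 80% power. It does not: step 7 reproduces that figure, and the current rule gives about 89% for any definition at season end.
- A reader might take the 10 points of step 4 as the trial's loss. They belong to one optional interim look, which exists only if recruitment spreads to the Southern Hemisphere. Missing it leads on to the season-end analysis.
- A reader might say the unused error protects nothing. Step 8 shows that it absorbs the approximation in the split between looks.

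Stratification and the offset do not remove the problem, because the number of vaccine cases remains an integer.

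**Conclusion.** The concern holds as a matter of efficiency. The current rule is valid and conservative: it uses 1.97% of 3.35% in the protocol's own example, and about 3.3% of 5% on average at a single season-end analysis. At VE 70% the avoidable loss is about 10 points at the example interim look, but about 1 to 2 points over the whole trial: 91.5% against 92.8% over both looks, or about 89% against 91% averaged over event totals at a single look. The power figures rest on equal VE across definitions, equal follow-up and pooled strata, and the two-look figure on the scaled counts of 20 and 36. A better rule is available from counts the plan already needs, so this is a cheap improvement and not a correction of an invalid test.

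**What to change.** In Section 11.4.1.1, keep one common cut-off but compute it from the exact joint null distribution of the nested case splits given the observed counts, enumerated within strata and with the follow-up offset to match the planned test.
- **Interim look:** take the largest common level whose exact probability of any success is within the interim budget.
- **Final look:** enumerate both looks jointly and take the largest level that keeps total exact error at or below 5%. Do not calibrate the final look on its own.
- **Worked example:** replace 0.0175 by p<0.0217, that is, at most 2/14, 4/18 or 7/25 vaccine cases, with exact error 2.97%.
- **Confidence intervals:** say that this same cut-off sets their level. At 0.0217 it is 1 − 2×0.0217 = 95.7%, against 1 − 2×0.0175 = 96.5% now. This has to be stated because a range of cut-offs gives the same decision rule.

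The cost is one reworded paragraph, slightly more programming at the time of analysis, and a smaller margin of unused error. No extra participants are needed.
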